2.11 Patient-reported outcomes

The EORTC QLQ-C30 questionnaire and the EQ-5D-5L will be used to collect patient's QoL data. The FAS will be used for analyzing PRO data. The global health status/QoL scale score of the QLQ-C30 and the health status index score of the EQ-5D-5L are identified as the primary patient-reported outcome variables of interest. Physical functioning, emotional functioning and social functioning scale scores of the QLQ-C30, and overall health status of the EQ-5D-5L are identified as secondary patient-reported QoL variables of interest.

High scores in the EORTC QLQ-C30 correspond to a higher response level. Thus a high score for a functional scale represents a high / healthy level of functioning; a high score for the global health status / QoL represents a high QoL, but a high score for a symptom scale / item represents a high level of symptomatology / problems. Higher scores in the EQ-5D-5L correspond to better health states or overall health status.

Established estimates for the minimal important differences (MID) for each measure will be used to interpret change from baseline scores. For the EORTC QLQ-C30 a change of ≥ 10 will be defined as the MID [Osoba 1998]. For the EQ-5D-5L, a change in the index score of ≥ 0.08 and a changes in the VAS of ≥ 7 will be defined as the MID [Pickard 2007].

EORTC QLQ-C30 subscale scores will be calculated by first obtaining the raw scores through adding up the item responses on the questions which make up each domain and then applying the linear transformation to the raw scores in accordance with the respective scoring manual provided by the developer (Fayers 2001). No imputation procedures will be applied for missing items or missing assessments.

For EQ-5D-5L health states will be converted to index value, during data analysis stage, based on the EQ-5D crosswalk value set for the UK using the time trade-off method (van Hout 2015). If any one of the five items is missing, the index value will be set to missing. In addition, the visual analog scale (ranging from 0 to 100) from the EQ-5D-5L will be evaluated for patient's rating of their overall health status.

The PRO instruments are planned to be administered during screening and every 8 weeks after first day of treatment during the first 12 months, and every 12 weeks thereafter until the end of treatment. PRO assessments will continue to be collected during the efficacy follow-up after the end of treatment.

The baseline is defined as the last PRO assessment on or before the first day of treatment.

Descriptive statistics will be used to summarize the PRO scores and change from baseline for scales of the EORTC QLQ-C30 and health states, overall health status, and index values of the EQ-5D-5L at each scheduled assessment time point by cohort. Data obtained after the end of treatment will be summarized separately. Additionally, analysis by responder/non-responder may be performed if sufficient number of responders is observed.

2.12 CgA and NSE

The biochemical response will be assessed using the change from baseline for CgA and NSE levels.

Change from baseline in CgA and NSE will be summarized using descriptive statistics for all patients. CgA and NSE values might be analyzed on the logarithmic scale if their observed distribution is found be right skewed.

[figure not shown]
Data handling principles

[figure not shown]
The lower limit of quantification (LLOQ) values for CgA and NSE will be specified by the laboratory running the assay.

Measures below the LLOQ will be handled as follows:

- If the proportion of measures below LLOQ is below 15%, all values specified as below LLOQ will be imputed by half of the LLOQ and the standard set of summary statistics will be used.
- If the proportion of measures below LLOQ is above 15%, but below 50%, an alternative choice of summary statistics requiring no imputation such as percentiles may be used.
- Otherwise the data will be missing
- When both baseline and post baseline values are below LLOQ, change from baseline will not be imputed and reported as missing.

All available data points obtained at scheduled and unscheduled visits will be considered for the analysis.

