1.2 Study objectives and endpoints

Objectives and related endpoints are described in [Table 1-1](#) below.

Table 1-1 Objectives and related endpoints

Objective	Endpoint
Primary	
To estimate the antitumor activity of PDR001 as a single agent in the well-differentiated NET and poorly-differentiated GEP-NEC groups	ORR (confirmed PR and CR) according to blinded independent review committee (BIRC) radiological assessment by RECIST 1.1
Key secondary	
To estimate efficacy of PDR001 in the well-differentiated NET and poorly-differentiated GEP-NEC groups	Duration of Response (DoR) by RECIST 1.1 and as per BIRC
Other secondary	
To assess the safety and tolerability of PDR001 in each group and in the overall study population	Frequency and severity of adverse events Other safety data as considered appropriate
To evaluate additional efficacy parameters in the well-differentiated NET and poorly-differentiated GEP-NEC groups	Disease Control Rate (DCR), Time to Response (TTR), PFS by RECIST 1.1 and as per BIRC Immune Response Criteria by irRECIST and as per BIRC (irORR, irDoR, irTTR, irDCR, irPFS) 1-year and 2-year overall survival (OS) rate
To evaluate biochemical response to treatment (based on CgA and NSE) in the well-differentiated NET and poorly-differentiated GEP-NEC groups	Changes from baseline in CgA and NSE
To characterize the pharmacokinetics of PDR001 with 400 mg flat dose Q4W in the well-differentiated NET and poorly-differentiated GEP-NEC groups	PK parameters (e.g. Ctrough)
To characterize patient's health-related quality of life with PDR001 in the well-differentiated NET and poorly-differentiated GEP-NEC groups	Global health status/QOL score of the EORTC QLQ-C30 and the index score of the EQ-5D-5L
To evaluate the prevalence and incidence of immunogenicity in the well-differentiated NET and poorly-differentiated GEP-NEC groups	Antidrug antibodies (ADA) prevalence at baseline and ADA incidence on-treatment

2 Statistical methods

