Quantitative data (e.g., age, body weight, etc.) will be summarized by appropriate descriptive statistics (i.e. mean, standard deviation, median, minimum, and maximum).

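### Setting the CgA/NSE change to missing when both values are below LLOQ removes near-zero changes, so the mean change is pushed away from zero, modestly and in either direction

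*SAP*

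**What the plan says.** SAP Table 1-1 lists the endpoint "Changes from baseline in CgA and NSE" under the other secondary objectives. SAP 2.12 sets the analysis: "Change from baseline in CgA and NSE will be summarized using descriptive statistics for all patients". The default statistics for quantitative data in SAP 2.1 are "mean, standard deviation, median, minimum, and maximum", and SAP 2.12 allows the log scale if the values prove right skewed.

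Values below LLOQ are handled by tier:
- Under 15% of measures below LLOQ: "all values specified as below LLOQ will be imputed by half of the LLOQ and the standard set of summary statistics will be used".
- Between 15% and 50%: "If the proportion of measures below LLOQ is above 15%, but below 50%, an alternative choice of summary statistics requiring no imputation", such as percentiles. This is optional.
- Remaining cases: "Otherwise the data will be missing".

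A last bullet, tied to no tier, reads: "When both baseline and post baseline values are below LLOQ, change from baseline will not be imputed and reported as missing". Protocol 10.5.6.1 has the same bullets, and SAP section 4 lists no departure on this point. No LLOQ is stated: "The lower limit of quantification (LLOQ) values for CgA and NSE will be specified by the laboratory running the assay".

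**The concern.** In the lowest tier the last bullet undoes the imputation for one kind of pair only. Half the LLOQ at both times gives a change of 0, and those are the pairs removed.

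For a patient below LLOQ at baseline, inclusion then depends on the outcome. If the marker becomes measurable, the patient is kept, with a rise. If it stays unquantifiable, the patient leaves the summary at that visit. A patient who falls from measurable to below LLOQ is kept. The summary is described as covering all patients, but it covers only pairs with at least one quantifiable value.

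The trial has one arm, so no control group carries the same selection. The SAP plans no count of the removed pairs, no shift table and no sensitivity analysis for this endpoint, so the loss would not show in the summary table.

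**Working it through.** The plan gives no expected change, variability or share below LLOQ for these markers, so there is no figure of its own to reproduce. The shares and distributions below are assumptions.

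**1. Patients starting below LLOQ.** Baseline is imputed at 0.5 LLOQ. The pair is kept only if the later value is at least 1 LLOQ. Every retained change is therefore at least 1 - 0.5 = +0.5 LLOQ.

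**2. Effect on the overall mean.** Let n be the number of pairs, k the share with both values below LLOQ, and S the sum of changes. Under half-LLOQ imputation the both-below pairs add 0 to S.
- All pairs kept: S/n.
- Plan's rule: S/(n(1-k)).
- Ratio: 1/(1-k), whatever the sign of S.

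| k | 1/(1-k) |
|---|---|
| 2% | 1.02 |
| 5% | 1.05 |
| 10% | 1.11 |
| 14% | 1.16 |
| 15% | 1.18 |

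A both-below pair uses two below-LLOQ measures. If under 15% of the measures in the same pairs are below LLOQ, k is also under 15%, hence the ceiling of about 1.18. SAP 2.12 does not say whether the 15% is judged by visit, by marker or pooled.

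**3. Worked example.** Take n = 95, the well-differentiated group (protocol 1.2.1.2). Assume 13 patients are below LLOQ at baseline, of whom 10 stay below and 3 rise to 1.5 LLOQ. Measures below LLOQ: (13 + 10)/190 = 12.1%, so the lowest tier applies.
- Starting below LLOQ: 3 × 1.0/3 = +1.00 LLOQ under the rule, against 3 × 1.0/13 = +0.23 LLOQ with all kept.
- Other 82 average -1 LLOQ: (-82 + 3)/85 = -0.929 under the rule, against -79/95 = -0.832.
- Other 82 average +1 LLOQ: 85/85 = +1.000, against 85/95 = +0.895.
- Ratio in both directions: 95/85 = 1.118.

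**4. Which is nearer the truth on the raw scale?** Simulated log-normal pairs, log SD 1, correlation 0.9, 10% of baselines below LLOQ; mean change in LLOQ units:

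| Log shift | Share dropped | True | Half-LLOQ, all kept | Plan's rule |
|---|---|---|---|---|
| -0.3 | 8.6% | -1.531 | -1.537 | -1.683 |
| +0.3 | 4.7% | +2.085 | +2.091 | +2.194 |

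The formula agrees: -1.537/(1 - 0.086) = -1.682 and 2.091/(1 - 0.047) = 2.194. With no shift, both methods give 0.002, the true value.

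A second model (baseline log SD 1.5, log-change SD 0.5, 14% of baselines below LLOQ, log shift +0.20; unit = median baseline) gives a raw mean of 1.183 true, 1.184 all kept and 1.322 under the rule. The raw median is 0.118, 0.129 and 0.197.

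**5. Log scale, second model.** The median log change is 0.200 true, 0.150 with both-below pairs set to a log ratio of 0, and 0.226 under the rule. With a true shift of -0.20 the mean log change is -0.179 with zeros and -0.205 under the rule. Forcing zeros does not reliably help on this scale.

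**The case against.** The strongest reply has four parts.

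- **The rule is a deliberate exception.** It is prespecified and identical in both documents, and the protocol keeps below-LLOQ values visible as such in listings. This is true, but a listing does not correct a mean described as covering all patients.
- **A both-below pair is doubly censored, so its direction is unknown.** On the raw scale the change is still bounded within one LLOQ of zero, and 0 is what the plan's own imputation implies. On the log scale there is no bound, and the objection stands. At 30% below LLOQ with a true shift of -0.20, zero-filling gives a median log change of 0.000, against -0.184 under the rule. It would also impute in a tier reserved for statistics that need no imputation.
- **Nothing shows that the rule will bite.** The share below LLOQ is not given, and if it is near zero the effect is too. This stands.
- **No decision depends on it.** The endpoint has no test or threshold. This stands.

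A reader might also infer that the rule biases the mean change upward. The documents do not support that: patients who fall below LLOQ are kept, so the overall mean moves away from zero in whichever direction it already lies. The upward bias is certain only among patients who start below LLOQ, and no summary of that subset is planned. Nor do inflations of 30% or more apply where means are prescribed. They need about 30% of values below LLOQ, where the plan points to percentiles.

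**Conclusion.** The point holds in a limited form. In the under-15% tier, the last bullet contradicts the plan's own imputation, makes inclusion depend on the outcome for patients starting below LLOQ, and moves the overall mean away from zero by 1/(1-k). On the raw scale, keeping the pairs was closer to the truth for rises and falls in the cases simulated.

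The size is modest: at most about 18% relative, provided the 15% is judged on the same pairs, and little or nothing with few values below LLOQ or no net change. It rests on an assumed share below LLOQ and, for the comparison with the truth, on log-normal markers. The endpoint is descriptive, and the success criterion on response rate is untouched.

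**What to change.** In SAP 2.12, and in protocol 10.5.6.1 or as a recorded departure in SAP section 4:

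1. **Under-15% tier, raw-scale change:** delete the last bullet. Half-LLOQ imputation then gives a both-below pair a change of 0, and the pair stays in the summary.
2. **Log scale, and the 15% to 50% tier:** do not force a log ratio of 0. At each visit, report the number of both-below pairs as having no quantifiable change, for example in a shift table beside the summary.
3. State whether the 15% and 50% limits are judged by marker, by visit or pooled.

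The cost is a few lines of text, one line of code for the summary and a small count table, with no new data. The downside is a convention: zero stands in for changes known only to lie within one LLOQ of zero.

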2.14 Interim analysis

An interim analysis for preliminary assessment of PDR001 in this patient population will be conducted once at least 30 patients from the well-differentiated NET group have 3 radiological assessments (week 24) or have discontinued study for any other reason. All available efficacy and safety data from the well-differentiated NET and poorly-differentiated GEP-NEC groups up to the cut-off date will be used for IA. The study will not be stopped at the interim analysis for efficacy reasons regardless of efficacy results and will continue until mature data for all patients become available.

3 Sample size calculation

Group 1: Well-differentiated NET

In the absence of an established control treatment, ORR reported in the placebo arms of studies reported in Table 1-1 of the protocol can serve as a reference. A 3% ORR is therefore considered as a reasonable reference while an improvement up to 10% is considered as clinically meaningful in this patient population.

Total sample size of 90 patients was chosen such that with an observed 10% response rate, the corresponding 95% CI excludes the value 3%.

Approximately thirty patients will be recruited in each cohort NET cohort: pancreatic, GI and thoracic.

Operating characteristics in the well-differentiated NET group are given in [Table 3-1](#). A sample size of 90 patients ensures a 90% probability of success if the true ORR is 15%.

Table 3-1 Operating characteristics for the full population

True response rate	Probability of observing 10% or more responders at the end of the study*
10%	0.55
11%	0.67
12%	0.77
13%	0.84
14%	0.90

15%	0.94
-----	------

In addition, [Table 3-2](#) shows the probability of observing at least 3 responders in a cohort with 30 patients under the assumption of true response rate of 10-20% in this cohort.

Table 3-2 Probability of observing at least 3 responders in a cohort with more than 10% true response rate

True response rate in a cohort	Probability of observing 3 or more responders in a cohort with 30 patients end of the study*
10%	0.59
12%	0.72
14%	0.81
16%	0.88
18%	0.93
20%	0.96

Group 2: Poorly-differentiated GEP-NEC

Approximately 20 patients will be enrolled in the poorly-differentiated GEP-NEC group. The operating characteristics are shown in Table 3-3 and Table 3-4. With the planned sample size the probability to observe at least moderate efficacy ($\geq 10\%$ ORR) is more than 80% if the true ORR is 15%. Posterior probability of a true ORR of at least moderate efficacy was computed for different scenarios assuming a minimally informative prior with Beta distribution and the following parameters: $a=0.176$, $b=1$. Posterior probability of a true ORR to be $\geq 10\%$ ORR is more than 70% if 3 responders are observed in 20 patients.

Table 3-3 Operating characteristics for the poorly-differentiated GEP-NEC group

True response rate	Probability of observing 2 or more responders ($\geq 10\%$ ORR) in 20 patients	Probability of observing 3 or more responders ($\geq 15\%$ ORR) in 20 patients
10%	0.61	0.32
12%	0.71	0.44
15%	0.82	0.60
18%	0.90	0.73
20%	0.93	0.79

Table 3-4 Posterior probability of a true ORR in the poorly-differentiated GEP-NEC group corresponding to at least moderate efficacy ($\geq 10\%$ ORR)

Number of observed responders in 20 patients	Posterior probability for a true ORR $\geq 10\%$
1	15.8%
2	44.0%
3	71.4%
4	88.6%

4 Change to protocol specified analyses

5 No probabilistic evaluation of heterogeneity between three cohorts in the well-differentiated NET group will be performed. No other changes to the protocol specified analyses are included in this analysis plan. Appendix

5.1 Imputation rules

5.1.1 Study drug

The following rule should be used for the imputation of the dose end date for a given study treatment component:

Scenario 1: If the dose end date is completely missing and there is no EOT page and no death date, the patient is considered as on-going:

The patient should be treated as on-going and the cut-off date should be used as the dose end date.

Scenario 2: If the dose end date is completely or partially missing and the EOT page is available:

Case 1: The dose end date is completely missing, and the EOT completion date is complete, then this latter date should be used.

Case 2: Only Year(yyyy) of the dose end date is available and $yyyy < \text{the year of EOT date}$:

Use Dec31yyyy

Case 3: Only Year(yyyy) of the dose end date is available and $yyyy = \text{the year of EOT date}$:

Use EOT date

Case 4: Both Year(yyyy) and Month (mm) are available for dose end date, and $yyyy = \text{the year of EOT date}$ and $mm < \text{the month of EOT date}$:

Use last day of the Month (mm)

All other cases should be considered as a data issue and the statistician should contact the data manager of the study.

After imputation, compare the imputed date with start date of treatment, if the imputed date is $<$ start date of treatment:

Use the treatment start date

Patients with missing start dates are to be considered missing for all study treatment component related calculations and no imputation will be made. If start date is missing then end-date should not be imputed.

5.1.2 AE, ConMeds and safety assessment date imputation

Table 5-1 Imputation of start dates (AE, CM) and assessments (LB, EG, VS)

Missing Element	Rule
day, month, and year	
 No imputation will be done for completely missing dates
day, month	
 If available year = year of study treatment start date then 
 If stop date contains a full date and stop date is earlier than study treatment start date then set start date = 01JanYYYY Else set start date = study treatment start date. If available year > year of study treatment start date then 01JanYYYY If available year < year of study treatment start date then 01JulYYYY
day	
 If available month and year = month and year of study treatment start date then 
 If stop date contains a full date and stop date is earlier than study treatment start date then set start date= 01MONYYYYY. Else set start date = study treatment start date. If available month and year > month and year of study treatment start date then 01MONYYYYY If available month and year < month year of study treatment start date then 15MONYYYYY

Table 5-2 Imputation of end dates (AE, CM)

Missing Element	Rule (* = last treatment date plus 150 days not > (death date, cut-off date, withdrawal of consent date))
day, month, and year	
 Completely missing end dates (incl. ongoing events) will be imputed by the end date of the on-treatment period*
day, month	
 If partial end date contains year only, set end date = earliest of 31DecYYYY or end date of the on-treatment period *
day	
 If partial end date contains month and year, set end date = earliest of last day of the month or end date of the on-treatment period*

Any AEs and ConMeds with partial/missing dates will be displayed as such in the data listings.

Any AEs and ConMeds which are continuing as per data cut-off will be shown as 'ongoing' rather than the end date provided.

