7.2.6.6.1 Hematology

Hematology tests are to be performed at each scheduled visit as indicated in [Table 7-1](#) and [Table 7-4](#). Lab assessment done ≤ 4 days before first dose of study treatment are permitted to be used as Cycle 1 Day 1 labs and do not need to be repeated. Hematocrit, Hemoglobin, Platelets, Red blood cells, White blood cells, Differential (Basophils, Eosinophils, Lymphocytes, Monocytes, Neutrophils, Bands, Other) will be measured.

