For safety and efficacy evaluations, the last available assessment on or before the date of start of study treatment is defined as “baseline” assessment.

If patients have no value as defined above, the baseline result will be missing.

On-treatment assessment/event and observation periods

For adverse event reporting the overall observation period will be divided into three mutually exclusive segments:

1. ***pre-treatment period***: from day of patient’s informed consent to the day before first administration of study treatment
2. ***on-treatment period***: from date of first administration of study treatment to 30 days after date of last actual administration of any study treatment (including start and stop date)
3. ***post-treatment period***: starting at day 31 after last administration of study treatment.

Safety summaries (tables, figures) include only data from the on-treatment period with the exception of baseline data which will also be summarized where appropriate (e.g. change from baseline summaries). In addition, a separate summary for death including on treatment and post treatment deaths will be provided. In particular, summary tables for adverse events (AEs) will summarize only on-treatment events, with a start date during the on-treatment period (***treatment-emergent*** AEs).

Additional summaries will be displayed to report deaths, all AEs, AEs related to study treatment, all SAEs and SAEs related to study treatment collected up to 150 days after last administration of PDR001.

However, all safety data (including those from the post-treatment period) will be listed and those collected during the pre-treatment and post-treatment period will be flagged.

Last contact date

The last contact date will be derived for patients not known to have died at the analysis cut-off using the last complete date among the following:

Table 2-1 Last contact date data sources

Source data	Conditions
Last contact date/last date patient was known to be alive from Survival Follow-up page	- Patient status is reported to be alive, lost to follow-up or unknown.
Start/End dates from further antineoplastic therapy	Non-missing medication/procedure term.
Start/End* dates from drug administration record	Non-missing dose. Doses of 0 are allowed.
End of treatment date from end of treatment page	No condition.
Tumor (RECIST/irRECIST) assessment date	Evaluation is marked as 'done'.

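### SAP Table 5-1 dates some partially dated lab, ECG and vital-sign values to the first-dose day, which puts them in the baseline window and outside the post-baseline safety summaries (minor)

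*SAP*

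**What the plan says.** Table 5-1 in SAP 5.1.2 carries the title "Imputation of start dates (AE, CM) and assessments (LB, EG, VS"). Its rules for a partial date are:

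- **Known part matches first dose** (month and year if the day is missing; year alone if day and month are missing). One branch avoids the first-dose date, and it starts "If stop date contains a full date and stop date is earlier than study treatment start date". Otherwise: "Else set start date = study treatment start date".
- **Later month:** "If available month and year > month and year of study treatment start date then 01MONYYYYY".
- **Later year:** "If available year > year of study treatment start date then 01JanYYYY".
- **Nothing known:** "No imputation will be done for completely missing dates".

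An earlier month or year is set to a date before first dose.

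On baseline, SAP 2.1.1 says that "the last available assessment on or before the date of start of study treatment is defined as" the baseline assessment. It gives no time-of-day rule and no rule for two values dated on the same day. The same section starts the on-treatment period on the first-dose day.

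SAP 2.8.3 reports the worst post-baseline lab grade, worst post-baseline liver values, shift tables from baseline to the worst on-treatment value, and a listing of grade 3 and 4 lab toxicities. SAP 2.8.4 uses changes from baseline for ECG and vital signs.

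Protocol 7.2.6.6.1 adds: "Lab assessment done ≤ 4 days before first dose of study treatment are permitted to be used as Cycle 1 Day 1 labs". Protocol 7.2.6.6.2 says the same for chemistry.

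**The concern.** For an adverse event, setting an uncertain start date to first dose is conservative, because the event becomes treatment-emergent. For a measurement the same step works the other way, because the first-dose day belongs to the baseline window. A value obtained after dosing can then be treated as a pre-treatment reference and is no longer dated after baseline.

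At stake is the accuracy of individual rows in the safety summaries. An abnormal post-dose value could disappear from a worst post-baseline table, or hide its own shift by becoming the reference. The records most open to partial dates are probably local ones: SAP 2.8.3 pools local with central laboratory data, and ECGs are collected and read locally. The SAP already gives tumour assessments their own date rule (5.1.2.1), so treating assessments apart from event start dates is not foreign to the plan.

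**Working it through.** There is no planned figure to reproduce. The check follows the rules through, then gauges how often they would act on a value whose date is already partial.

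**Rule chain for a lab, ECG or vital-sign reading**

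1. The title of Table 5-1 includes it.
2. It has no stop date, so the branch that needs a full stop date before treatment cannot apply.
3. If the known part of the date matches first dose, the date becomes the first-dose date.
4. That date meets the baseline definition in SAP 2.1.1 and is not after baseline.

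**Worked dates, first dose 5 June 2017**

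| True date | Missing | Imputed date | Result |
|---|---|---|---|
| 20 Jun 2017 | day | 5 Jun 2017 | baseline window |
| 3 Jul 2017 | day | 1 Jul 2017 | post-baseline |
| 20 Dec 2017 | day and month | 5 Jun 2017 | baseline window, 198 days early |
| 15 Jan 2018 | day and month | 1 Jan 2018 | post-baseline |

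**Illustrative lab case.** First dose is 12 June 2017. The Cycle 1 Day 1 chemistry was drawn on 9 June (3 days earlier, within the 4 allowed) with ALT 30 U/L, which is grade 0 against the upper limit of 35 in SAP Table 5-3. An unscheduled post-dose ALT of 400 U/L is dated only June 2017. 400/35 = 11.4 times the upper limit, which is grade 3 (above 5 and up to 20 times). The imputed date is 12 June. No genuine value carries that date, so 400 U/L becomes baseline. The grade 0 to grade 3 shift then has a grade 3 starting point and shows no increase.

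**How often, given a partial date.** Assumptions, for scale only: first doses uniform over 14 February to 20 September 2017 (first consent and end of recruitment as proxies; 219 dates), and visits every 28 days up to the 10 August 2018 cut-off.

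*Day missing:*

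- Cycle 2 Day 1 at +28 days stays in the first-dose month only if dosing began on day 1 to 3 of a 31-day month or day 1 to 2 of a 30-day month. For March to September that is 3+2+3+2+3+3+2 = 18 dates, and 18/219 = 8%.
- At the -7 day limit of the visit window it is 67/219 = 31%; at the +7 day limit, 0%.
- Scheduled visits from Cycle 3 onward: 0%.
- All scheduled visits after Cycle 1: 18/3281 = 0.5%.
- Unscheduled values on days 1 to 27 after first dose: 3192/(219 × 27) = 3192/5913 = 54%.
- No value from a later month was imputed to first dose or before.

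*Day and month missing:* every value in the calendar year of first dose is moved. Over all scheduled visits this is 1545/3281 = 47%.

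These shares are conditional on the date being partial. They are not the proportion of all records affected, which the documents do not allow anyone to calculate.

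**The case against.** A reader might infer that any partially dated on-treatment value goes to first dose, replaces the true baseline and vanishes from toxicity reporting. The documents do not support that, for these reasons:

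- **The rule is conditional.** Later months and years stay after first dose, and fully missing dates are left alone.
- **Replacement is not certain.** The 4-day allowance does not cover ECG or vital signs. Protocol Table 7-6 schedules a pre-dose ECG every 12 weeks from Cycle 1 Day 1, and Table 7-1 schedules vital signs that day. A genuine same-day value should normally exist, which gives a tie, not a replacement. The same holds for labs drawn on Day 1.
- **The value does not disappear everywhere.** The on-treatment period includes the first-dose day, so shift tables do not clearly exclude a moved value. Grade 3 and 4 labs remain in the listing.
- **Other routes capture serious cases.** A lab abnormality that requires a change in study treatment is an adverse event (Protocol 8.1.1 and 8.1.2.1), and Protocol Table 6-3 attaches a treatment consequence to an ALT at the level in the example. Where a local test is done, a parallel sample should go to the central laboratory (Protocol 7.2.6.6).
- **Partial dates should be rare.** Missing values are queried and central results arrive electronically (Protocol 9.4), and ECG tracings should carry a date.

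All of this stands, and it limits the size of the problem. It does not remove the error. In the matching case the stated rule still takes a post-dose value out of the worst post-baseline tables. Counting it on-treatment does not help when it has also become the baseline, and in a tie the outcome is left to the programmer.

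**Conclusion.** The point holds in a limited form, at minor severity. A post-dose lab, ECG or vital-sign value whose partial date matches the first-dose month and year, or the first-dose year when the month is also missing, is placed in the baseline window. It is lost from the worst post-baseline grade and liver summaries. It can become baseline when nothing genuine is dated that day, most plausibly for labs drawn up to 4 days before dosing. Otherwise the choice of baseline is undefined.

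The most exposed values are unscheduled ones in the first four weeks with the day missing, and any value in the first-dose year with day and month missing. The actual count of such dates is unknown and probably small. The conclusion rests on the wording of the SAP alone; the percentages also rest on the uniform-enrolment assumption. The primary endpoint, response rate, is not affected.

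**What to change.** Remove labs, ECGs and vital signs from Table 5-1 and give them their own row, with the period assigned from the recorded visit:

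- Records labelled screening or Cycle 1 Day 1 pre-dose, records from a known earlier month or year, and records documented as pre-dose stay pre-treatment.
- Only post-dose or undetermined records in the matching month or year are dated no earlier than the day after first dose, flagged, counted as post-baseline and not used as baseline.
- On Day 1, a value with a complete pre-dose date takes precedence over an imputed one.

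The limits in the first two items matter. Protocol 7.1.2 allows repeat lab tests during screening, and sending every unlabelled record to post-baseline would misclassify such repeats.

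The cost is one SAP row, one sentence added to the baseline definition and a small programming change. The downside is that a few undetermined pre-dose values may be counted as post-baseline, which is the conservative direction for safety.
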